Aim 2: Evaluate the impact of intervention condition on eating disorder symptoms. Hyp 2a. Participants in peer mentorship will have greater reductions in eating disorder symptoms, measured using the Eating Disorder Symptom Inventory (EPSI), compared to both control conditions. Hyp2b: For individuals who meet criteria for current or past anorexia nervosa, individuals assigned to peer mentorship will be more likely to achieve or maintain a BMI ≥ 18.5 , compared to both control conditions. Hyp2c: For individuals who meet criteria for current or past bulimia nervosa or binge eating disorder, individuals assigned to peer mentorship will be more likely to abstain from bingeing/purging and bingeing episodes, respectively, compared to individuals in either control condition.

Aim 3: Evaluate the impact of intervention condition on total cost for eating disorder treatment. Hyp 3. Estimated total cost for eating disorder treatment, measured using the Healthcare Utilization Survey, will be lower among peer mentorship participants compared to both control groups at (i) post-treatment and (ii) one-year follow up.

Exploratory Aim: Evaluate characteristics of individuals participating as peer and social support mentors. Exploratory hypothesis: Mentor characteristics and similarity between mentee and mentor characteristics will not influence mentee outcomes (acceptability, eating disorder symptoms, and estimated treatment cost).

Inclusion/Exclusion Criteria

This section details your study sample(s) and addresses the requirement for risk minimization. You may choose to divide your sample by population (healthy controls vs. subjects) or by procedure (subjects who will have an MRI) and then define different sets of criteria for each.

For each sample, create or insert a table to describe detailed criteria for study inclusion and exclusion and the method you will use to ascertain each criterion. The method of ascertainment may describe tests, scales and instruments. When relevant, indicate the level of training of the person who will make the assessment (e.g. clinical interview by a psychiatrist).

Inclusion/Exclusion Criteria needs to be numbered and listed in outline form (see Table template below)

Mentees (Adolescents or adults with anorexia nervosa, bulimia nervosa, or binge eating disorder):

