**Note that all EDRU screens will be reviewed with a clinician (MD or PhD level) and if any criteria are in question, the clinician will speak directly with the potential participant by telephone.*

CRITERION	METHOD OF ASCERTAINMENT
Inclusion:	
1. Ages 14 – 45 years	Initial telephone interview with Project HEAL staff, confirmation during telephone screening with EDRU research team member (RA level or higher)*
2. Meets criteria for current or past anorexia nervosa, bulimia nervosa , or binge eating disorder (criteria met either presently or at time of entry into treatment for most recent treatment course)	Eating Disorder Assessment -5 (administered by EDRU RA* during telephone screening)
3. Recent (within past 6 m) discharge from inpatient, residential, or partial hospitalization program (PHP)	Initial telephone interview with Project Heal staff, confirmation during telephone screening with EDRU RA*
4. Involved in outpatient treatment at an appropriate level of care	Telephone screening with EDRU RA* and Documentation from primary outpatient clinical provider using Provider Form
5. Medical stability	Telephone screening with EDRU RA* and Documentation from primary outpatient clinical provider using Provider Form
6. Access to Smart Phone or computer to complete study assessments	Telephone screening
Exclusion:	
1. Evidence of needing specialized treatment for another medical or mental health condition or substance use	Telephone screening with EDRU RA*

Mentors:

Mentors in the peer-mentorship group are adults who have recovered from an eating disorder, while mentors in the social support group are adults who never had an eating disorder. All mentors are individuals recruited and trained by Project Heal to do volunteer work within their organization.

Inclusion/Exclusion criteria:

CRITERIA	METHOD OF ASCERTAINMENT
Inclusion	
1. Participating as a peer or social support mentor in Project HEAL intervention	1. Weekly telephone supervision with mentors
Exclusion	
1. Not being a mentor	1. Same as above

Study Procedures

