Cover page

Official Title: Evaluation of the Communities of HEALing mentorship/support group program:
Assessment of preliminary efficacy

NCT number: NCT03317379

Document date: 3/23/2018

Statistical Analysis Plan

Intent-to-treat analyses will be used. Linear mixed models will be used to examine the relationship between group (peer, social support, wait list) and each outcome. Predictors in each model will be time, group, and their interaction. For all models, a random intercept will be included. The need for random slopes will be evaluated by examining model fit indices and testing the significance of the difference of the covariance estimate from zero. The peer group will be coded as the reference group to provide estimates and significance values for the difference between peer mentorship and each control condition.

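### Hyp 2b and 2c merge reaching and keeping the target in one yes/no endpoint, and the SAP neither adjusts for nor reports by status at entry

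*Protocol*

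**What the plan says.** **Endpoints (Protocol, Specific Aims and Hypotheses, Aim 2).** Hyp 2b states: "For individuals who meet criteria for current or past anorexia nervosa, individuals assigned to peer mentorship will be more likely to achieve or maintain". Its target is BMI 18.5 or above, and peer mentorship is set against each of the two control arms. Hyp 2c is framed by "For individuals who meet criteria for current or past bulimia nervosa or binge eating disorder" and predicts that peer mentees "will be more likely to abstain from bingeing/purging and bingeing episodes, respectively, compared to individuals in either control condition". Neither hypothesis defines success by where the person started, and neither names a time point.

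**Who can enter (Protocol, Inclusion/Exclusion Criteria, Mentees).** Criterion 2 accepts a diagnosis with "criteria met either presently or at time of entry into treatment for most recent treatment course". Criterion 3 requires discharge from inpatient, residential or partial hospital care within the past six months. Criterion 5 requires medical stability.

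**Allocation (Protocol, Study Procedures, Interventions).** The research team develops and runs the randomization scheme. No stratification factor is stated.

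**Analysis (SAP).** One paragraph prescribes a linear mixed model for every outcome: "Predictors in each model will be time, group, and their interaction". A random intercept is always included and random slopes are added if needed. The SAP names no entry-status covariate or stratum and no separate model for yes/no outcomes. It does not say whether the pre-randomization measurement is a level of time.

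**The concern.** Someone who enters with a past diagnosis, already at BMI 18.5 or above or already abstinent, can only keep or lose that status. Someone below target can only gain it or not. The first is relapse prevention and the second is recovery, and their rates are likely to differ. One yes/no outcome covers both.

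Three things are at stake:

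- **Precision.** If entry status predicts the outcome, leaving it out of the model leaves avoidable noise in the arm comparison.
- **Chance imbalance.** Hyp 2b and 2c are tested in diagnostic subgroups of a three-arm trial planned for 80 completers. At that size, arms can easily differ in the share already at target.
- **Interpretation.** The Protocol's background section motivates the trial by relapse after discharge, while its recruitment section speaks of promoting recovery. A pooled result cannot say which of the two mentorship affects.

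**Working it through.** **Figures in the plan.** The only sample-size figures are 80 mentee completers and 100 enrolled. There is no power statement, event rate or diagnosis mix to reproduce. Every rate below is an assumption.

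**Inputs.** b = share at target at entry; m = P(success | at target); a = P(success | below target). Illustration: b = 0.5, m = 0.85, a = 0.25. The assumed range is b from 0.3 to 0.7, with m/a from 0.80/0.40 to 0.90/0.20.

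**Per-person variance under three analyses**, with p = bm + (1−b)a:

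- Raw month-6 proportion: p(1−p)
- Change from baseline: b(1−b) + p(1−p) − 2(bm − bp)
- Conditional on entry status: bm(1−m) + (1−b)a(1−a)

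Illustration: p = 0.425 + 0.125 = 0.55.

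- Raw: 0.55 × 0.45 = 0.2475
- Change: 0.25 + 0.2475 − 2(0.425 − 0.275) = 0.1975
- Conditional: 0.5 × 0.1275 + 0.5 × 0.1875 = 0.1575

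The reduction is 1 − 0.1575/0.2475 = 36% against raw and 1 − 0.1575/0.1975 = 20% against change.

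| b | m / a | Raw | Change | Conditional | Gain vs raw | Gain vs change |
|---|---|---|---|---|---|---|
| 0.3 | 0.80 / 0.40 | 0.2496 | 0.2916 | 0.2160 | 13.5% | 25.9% |
| 0.5 | 0.80 / 0.40 | 0.2400 | 0.2900 | 0.2000 | 16.7% | 31.0% |
| 0.5 | 0.85 / 0.25 | 0.2475 | 0.1975 | 0.1575 | 36.4% | 20.3% |
| 0.3 | 0.90 / 0.20 | 0.2419 | 0.1579 | 0.1390 | 42.5% | 12.0% |
| 0.6 | 0.90 / 0.20 | 0.2356 | 0.1396 | 0.1180 | 49.9% | 15.5% |

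Over the range, the gain is about 13–50% against raw and 12–31% against change.

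**Effect of a chance imbalance.** Suppose one arm has 15 points more people at target.

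- Raw scale: 0.15 × (0.85 − 0.25) = +9 points in the arm difference.
- Change scale: subtract the baseline difference itself, 0.09 − 0.15 = −6 points.

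The SAP does not say which of these its model is closer to, and the two have opposite signs.

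**How likely is such an imbalance?** Assume equal arms and half of completers with anorexia nervosa: 80/3 × 0.5 ≈ 13 per arm. With b = 0.5, a gap of at least 15 points means a difference of 2 or more people out of 13. If X₁ and X₂ are the numbers at target, X₁ − X₂ + 13 follows Binomial(26, 0.5), so the probability is 1 − (0.155 + 2 × 0.144) ≈ 56%.

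**Simulation, 13 per arm, b = 0.5, no true effect.** The table gives the SD of the month-6 arm difference.

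| m / a | Unadjusted | Change | Adjusted for entry status |
|---|---|---|---|
| 0.70 / 0.40 | 0.195 | 0.231 | 0.190 |
| 0.80 / 0.25 | 0.195 | 0.186 | 0.167 |
| 0.90 / 0.10 | 0.197 | 0.124 | 0.120 |

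The mean difference was about zero in every case. Adjustment was at least as precise as either alternative throughout; change from baseline was not always better than the raw comparison.

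**Simulation of a SAP-type model** (linear, random intercept only, baseline as month 0, 13 per arm, 250 runs, no true effect). The mean effect was −0.01, but the estimate moved by −0.43 per unit of baseline imbalance (correlation −0.45). This matches the change-scale result: month-6 success was 0.81 if at target at entry and 0.24 if below, and 0.81 − 0.24 − 1 = −0.43.

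**The case against.** **The endpoint is a deliberate and legitimate choice.** Achieve or maintain is written openly into Hyp 2b, and being at or above a threshold at the end is a valid state endpoint in a randomized trial. This stands. The point concerns how the endpoint is analysed and reported, not whether it may be used. Splitting it would leave about 6 or 7 people per arm in each part (13/2), so the parts cannot carry the test.

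**Stronger readings that a reader might infer, and that the documents do not support:**

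- *Success is largely fixed by baseline status.* No document gives the share at target at entry or any maintain or achieve rate. In the illustration entry status explains 36% of outcome variance. A wider set of assumptions (m/a from 0.70/0.40 to 0.90/0.10) gives 8% to 64%.
- *The SAP ignores baseline.* If month 0 is a level of time, the time-by-group term compares change from the starting point. The SAP is unclear on this, which is not the same as ignoring it.
- *The pooled comparison is biased.* Randomization keeps it unbiased on average, as the simulations confirm.
- *Baseline weight is not collected.* The text describes the baseline provider form in terms of level of care and stability, and mentions height and weight under monthly contact. The form itself (Appendix 3) is not in the material reviewed, so its content can only be confirmed.

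**Hyp 2c is less explicit.** It does not say achieve or maintain; the mix follows from its current-or-past population and criterion 2. That is enough for the point to apply, but it is an inference.

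**A covariate alone does not repair a linear model for a yes/no outcome.** This is correct, and the fix therefore covers both.

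**Conclusion.** The point holds. Both hypotheses can combine reaching and keeping the target, because the entry criteria permit both starting states, and the SAP does not adjust for, stratify by or report by entry status. The consequence is lost precision, exposure of small subgroups to chance imbalance, and a result that cannot separate recovery from relapse prevention. It is not systematic bias.

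The fairer size is the comparison with change from baseline, since the SAP's model may include month 0: a variance reduction of about 20%, and a −6 point shift for a 15-point imbalance. The 36% and +9 points apply only if the analysis amounts to a raw month-6 comparison. All of these rest on assumed rates, and the subgroup size rests on equal allocation and an assumed half of completers with anorexia nervosa. If entry status predicts the outcome only weakly, the gain over an unadjusted comparison is small (SD 0.195 to 0.190 at 0.70/0.40). The interpretation problem does not depend on these rates, provided that both kinds of entrant are enrolled.

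**What to change.** In the SAP, for Hyp 2b and 2c:

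1. Name the end of the six-month randomized phase as the time point. Wait-list participants are offered a mentor after that.
2. Use a model suited to a yes/no outcome, with pre-randomization status on the same criterion as a covariate: BMI at or above 18.5 (yes/no) for Hyp 2b and abstinent (yes/no) for Hyp 2c. Use measured status, not the current-or-past diagnosis label, since the two need not coincide.
3. Keep this adjusted pooled comparison as the test. Report arm results separately for those below target at entry (achieve) and those at target (maintain), marked as descriptive only.
4. State how the baseline measurement enters the model.

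In the Protocol, confirm that the baseline provider form records height and weight before randomization. Also confirm that the baseline survey includes the episode-frequency item, which Assessment Instruments describes only for the monthly reports.

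The cost is a little more analysis work and SAP wording, and possibly an added item on an existing form or survey. No visits or participants are added, and the BMI threshold and clinical procedures are untouched. The downside is that the achieve and maintain results will be imprecise.

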Based on epidemiologic studies, AN occurs overwhelmingly more often in women than men (9:1 ratio). Therefore, we expect that our sample will be comprised of 90% female and 10% male. No participants will be excluded on the basis of ethnicity or race. The sample is expected to resemble the demographic composition of the population of patients with anorexia nervosa and bulimia (approx. 60% Caucasian, 20% African-American, 20% Hispanic).

Mentors: Mentors who have recovered from an eating disorder serving as peer mentors are expected to resemble the demographic composition of the population of patients who have eating disorders described above. Mentors who are Project HEAL volunteers who have not personally struggled with an eating disorder are expected to resemble the demographic composition of the general population of the cities they represent.

Description of subject population

Mentees: Participants will be adolescents and adults (ages 14 - 45) with a diagnosis of anorexia nervosa, bulimia nervosa or binge eating disorder who have recently been discharged from treatment at a higher level of care including inpatient/partial hospitalization, residential, or intensive outpatient program. All patients will be involved in outpatient treatment at an appropriate level of care (as documented by the patient's outpatient clinician).

Mentors: Mentors in the peer-mentorship group are adults who have recovered from an eating disorder, while mentors in the social support group are adults who never had an eating disorder. All mentors are individuals recruited and trained by Project Heal to do volunteer work within their organization.

Recruitment Procedures

Describe settings where recruitment will occur

Recruitment will occur using Project HEAL's online and social media platforms and at settings where patients have received treatment for an eating disorder at a higher level of care (hospitalization, partial hospitalization programs, residential, and intensive outpatient programs).

How and by whom will subjects be approached and/or recruited?

Participants who anticipate being discharged from a higher level of care will be provided with information about the study by a member of his/her treatment team. Participants will be provided with EDRU contact information if they are interested in learning more about the study.

How will the study be advertised/publicized?

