Assessments: All participants will complete monthly assessments of eating disorder symptoms, eating disorder quality of life, and co-morbid psychiatric symptoms throughout the six month randomized phase and then again at a 12-month follow up time point. Participants assigned to the wait-list condition will also complete monthly assessments throughout the "open label" phase in which they are receiving mentorship. On a monthly basis, patients' treatment providers will be contacted in order to obtain the patient's current height/weight from which to calculate BMI. Patient questionnaires will be administered using Qualtrics, a HIPAA-compliant applications accessible by smart phone or computer. If, during participation in an intervention or wait-list condition, a participant is hospitalized or returns to a higher level of care (e.g., residential treatment, partial hospitalization), he/she may resume participation in the mentorship component of the study only with permission from his/her treatment provider (a new letter must be obtained from primary provider). **All participants will complete a questionnaire assessing study acceptability of the study at the end of the 6 months period of mentorship or as soon as their participation in the study ends (e.g., if a participant discontinues after 3 months, they will be asked to complete the survey at that time).**

Mentor Procedures:

Individuals participating as mentors will be asked if they are willing to allow the study team to utilize data previously collected as part of interviewing and training to be a mentor. This data includes demographic information such as age and gender, as well as diagnostic history, for the peer mentors. Mentors will be informed about the study during a supervision call with the PI of the study and Project HEAL staff. Prior to reviewing the consent form during the telephone call with all mentors, all mentors will be sent a copy of the consent form to review ahead of time. Mentors will be asked to then speak individually with one of the study team members (the PI, a trained RA or other study clinician) to indicate whether or not they wish to participate in the study.

The information collected as part of the process of interviewing to be a mentor will be sent in a de-identified format. The code linking mentor information with the identifier will be transmitted by phone to the study team. Mentors will also be asked to fill out a brief 4-question survey using Qualtrics.

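### Hyp 2b uses one fixed BMI cut-off of 18.5 for ages 14 to 45, so the outcome does not mean the same thing in growing adolescents as in adults and may misclassify some of them

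*Protocol*

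**What the plan says.** The protocol's Specific Aims and Hypotheses section places Hyp 2b under Aim 2, one of the primary aims. Its population is set by diagnosis alone: "For individuals who meet criteria for current or past anorexia nervosa". It predicts that, compared with either control condition, "individuals assigned to peer mentorship will be more likely to achieve or maintain a BMI" at or above a single stated number: "more likely to achieve or maintain a BMI ≥ 18.5". The same text appears in both copies of the protocol summary.

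The age range is set in the inclusion table ("1. Ages 14 – 45 years") and in the description of the subject population: "Participants will be adolescents and adults (ages 14 - 45) with a diagnosis of anorexia nervosa, bulimia nervosa or binge eating disorder". Minors are included by design, since the screening section sets out parental consent and assent for ages 14 to 17.

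On measurement, the Assessments paragraph says that each month "patients' treatment providers will be contacted in order to obtain the patient's current height/weight from which to calculate BMI". The Background section adds that weight and BMI trajectories will be evaluated. Neither place mentions a percentile, a z-score or any other reference to age.

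The SAP fits linear mixed models with time, group and their interaction as predictors. It contains no age covariate, age subgroup or sensitivity analysis, and it does not mention the 18.5 value. No stratification of the randomisation by age is stated.

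**The concern.** While a person is still growing, BMI has to be read against age and sex. A fixed value is therefore not the same weight status at 14 as at 30. Hyp 2b states the fixed value as the rule for its whole population, so this is a stated choice and not an omitted detail.

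Two things are at stake. First, a pooled percentage at or above 18.5 mixes two different quantities, and a reader cannot tell what a given figure says about recovery. Second, if some adolescents are classified by their age or growth instead of their clinical course, the outcome carries noise that pulls the arm difference toward zero. Hyp 2b can ill afford this. It uses only the anorexia nervosa subset of a three-arm study that requires 80 completers in all, or 80/3 ≈ 27 per arm before restriction by diagnosis.

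**Working it through.** **No figure to reproduce.** The documents give no power, effect size or expected rate for Hyp 2b. The only sample-size figures are 80 completers and 100 enrolled.

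**Step 1: can growth alone change the outcome?** BMI = weight / height². Take an assumed participant at 1.60 m and exactly BMI 18.5:

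- weight = 18.5 × 1.60² = 47.36 kg
- after 2 cm of growth at the same weight: 47.36 / 1.62² = 18.05
- after 3 cm: 47.36 / 1.63² = 17.83
- weight gain needed to stay at 18.5: 1.19 kg and 1.79 kg respectively

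This participant moves from success to failure through height alone. An adult of stable height cannot. No growth chart is needed to see this.

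**Step 2: size of the dilution (illustration only).** Let f be the adolescent share of the subset and D the true risk difference, assumed equal in adolescents and adults. Let Se and Sp be the sensitivity and specificity of the 18.5 rule in adolescents, the same in every arm, and assume adults are classified correctly. Then

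observed difference = (1 − f)·D + f·(Se + Sp − 1)·D = D·[1 − f·(2 − Se − Sp)].

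- Errors in one direction only, at rate m among those of that true status: Se + Sp = 2 − m, so the fraction retained is 1 − fm.
- Errors in both directions, each at rate m: Se + Sp = 2 − 2m, so the fraction retained is 1 − 2fm.

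The sample size for the same power rises by about 1 / (fraction retained)². All values of f and m are assumed:

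| f | m | Shrinkage, one way | Sample-size factor | Shrinkage, both ways | Sample-size factor |
|---|---|---|---|---|---|
| 0.10 | 0.10 | 1% | 1.02 | 2% | 1.04 |
| 0.25 | 0.30 | 7.5% | 1.17 | 15% | 1.38 |
| 0.40 | 0.50 | 20% | 1.56 | 40% | 2.78 |

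The lower right entry is an outer bound and not a plausible value: at m = 0.50 in both directions the rule would be a coin toss in adolescents.

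**Step 3: check on explicit rates.** Assume true success rates of 70% and 45%, f = 0.25, Se = 0.7 and Sp = 1.0:

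- arm 1: 0.75 × 0.70 + 0.25 × 0.7 × 0.70 = 0.6475
- arm 2: 0.75 × 0.45 + 0.25 × 0.7 × 0.45 = 0.4163
- difference = 0.231 against 0.25, a ratio of 0.925, as the formula gives

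The number per arm for 80% power rises from 61 to 72 (72/61 = 1.18), in line with the factor of 1.17. At 27 per arm, which overstates the subset, power falls from 46% to 40%.

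**The case against.** The strongest reply is that the cut-off is identical in all arms and allocation is randomised, so nothing favours one arm. That stands. A reader might infer that the rule biases the comparison; the documents do not support this. Chance age imbalance is possible in a small subset with no stated stratification, but that is a matter of precision and not of systematic bias.

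Next, every quantity in the illustration is assumed. The documents give no adolescent share, no anorexia nervosa share and no growth reference, and the protocol expects many mentor/mentee pairs to come from university communities, which hints at a low share. This also stands. A reader might infer that a known number of adolescents is misclassified, or in a known direction; neither can be derived. The growth example shows one mechanism, not a rate.

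Third, a continuous analysis of BMI trajectories is already planned. It avoids the cut-off, and the random intercept absorbs stable differences between people in BMI level. It does not repair the binary outcome, and raw BMI still carries growth during follow-up. A baseline-age covariate would not remove that growth either.

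Last, Hyp 2b is one of several hypotheses in a study of preliminary efficacy and covers one diagnostic group. That limits the weight of the point. It is no reason to leave the definition as it is.

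**Conclusion.** The point holds in a limited form. A single BMI value defines success across an age range that includes growing adolescents, and nothing in either document adjusts for age. The outcome therefore lacks one meaning across the subset and may misclassify some adolescents. The consequence to expect is dilution and a percentage that is hard to interpret. Hyp 2a, which rests on the EPSI, is untouched.

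The size cannot be fixed from the documents. The middle row of the table is a reasonable illustration, and it rests on the assumed f and m, on an equal true effect in adolescents and adults, and on equal error rates across arms. The case for change rests on the mixed meaning of the outcome, which needs none of these assumptions. The sponsor should make the change, but the point does not call the study's other conclusions into question.

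**What to change.** Before analysis, amend Hyp 2b and the SAP so that participants under 18 are classified by an age- and sex-referenced BMI (percentile or z-score). The sponsor should choose the reference and the threshold and fix both in advance. Keep the stated cut-off for adults. In the BMI trajectory analysis already planned, use age-referenced scores for minors.

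The cost is a short amendment to both documents, because the cut-off stands in the protocol and SAP wording alone would leave the two in conflict. The outcome definition then has two parts, which must be described when results are reported. No new data are needed: birth date and sex are recorded in the demographic form, and height and weight are requested from providers every month.
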